3.2 Exploratory Objective(s)

- 3.2.1 To assess adherence to referrals for supportive care resources (caregiver- and administrator-reported) among intervention caregivers (n = 20) and barriers to supportive care use among intervention and comparison (n=40) caregivers.
- 3.2.2 To obtain preliminary data on HNC caregiver outcomes (supportive care service use, perceived care quality, burden, and distress, quality of life, caregiving self-efficacy, and self-care) and HNC patient outcomes (physical well-being, unplanned healthcare utilization, perceived care quality, distress, and symptoms)..

CONNECTing Caregivers to Supportive Services (CONNECT):
A Technology-Based Intervention to Connect Cancer Caregivers with Supportive Care
Resources

Wake Forest Baptist Comprehensive Cancer Center
WFBCCC # 99519

- 3.2.3 To examine changes in the caregiver outcome variables (perceived care quality, burden, distress, quality of life, caregiving self-efficacy, and self-care) with changes in in supportive care resource use.
- 3.2.4 To examine if patient physical well-being and patient healthcare utilization are associated with change in caregiver burden and distress in intervention arm caregivers.
- 3.2.5 To characterize the correlation between caregivers and patients with regard to distress and perceived care quality.

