Comparison Arm. Caregivers not randomized to the intervention group will receive minimally enhanced usual care. This includes a generic (not tailored) printed list of hospital, community, and national supportive care resources (Appendix R). They will not receive the video, complete the web-based tool Preference survey, or have an option for an automated referral. The generic resource list will be printed for participants and emailed to them, if participants have an email address.

Data Collection Procedures. Data collection and instruments are reported in Table 2. At T0, patient and caregiver sociodemographics and caregiving characteristics will be collected and patient clinical information will be abstracted from the electronic health record (EHR) (Appendix S). Feasibility data will be collected throughout the study period (T0-T2). Caregivers and patients will complete self-report quantitative assessments at T0-T2 through REDCap. We will email or text a link to complete the REDCap surveys at the appropriate times. To minimize missing data, we will call any participant who fails to complete a survey within 48 hours of the link being sent. In the case that a patient dies, caregivers may choose whether or not continue in the study and complete follow up questionnaires.

Data Management. All screened and approached participants will be recorded in an Excel document Appendix M. The responses of anonymous refusal surveys (Appendices V and W) will be recorded in a separate REDCAP Refusal project. All completed surveys for consented patients and caregivers will be recorded in an third REDCap project.

CONNECTing Caregivers to Supportive Services (CONNECT):
A Technology-Based Intervention to Connect Cancer Caregivers with Supportive Care
Resources

Wake Forest Baptist Comprehensive Cancer Center
WFBCCC # 99519

Qualitative Data Collection: At 2-weeks post-intervention - T1, caregiver qualitative interviews will be completed in person (or by telephone, if participant prefers) to assess acceptability of the intervention (est. 30min) using semi-structured guides with open-ended questions (Appendix T). During interviews, CONNECT elements will be reviewed and open-ended questions will be used to elicit feedback on functionality, strengths, and weaknesses of the web-based tool. All interviews will be audio-recorded and transcribed verbatim.

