9.0 Statistical Considerations

Statistical Considerations. For the primary objective, the quantitative analyses will provide estimates of accrual, participation, and retention rates. For the secondary objectives, quantitative analyses will provide estimates of the mean and variance of CONNECT for acceptability and outcome variables to refine the protocol for a larger study. Though CONNECT is a caregiver-only intervention, analyses will also examine patient outcomes and relationships between caregiver and patient outcomes.

CONNECTing Caregivers to Supportive Services (CONNECT):
A Technology-Based Intervention to Connect Cancer Caregivers with Supportive Care
Resources

Wake Forest Baptist Comprehensive Cancer Center
WFBCCC # 99519

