9.2 Analysis of Exploratory Objectives

- 9.2.1 For Objective 2.2.1, frequencies will be used to summarize the number and type of referrals selected by intervention caregivers. Referral adherence will be defined as completion of referral (i.e. services utilized) within the caregiver's duration of study participation. Frequencies will also be used to summarize the number of intervention caregivers who adhered to referrals selected, among those who selected an automatic referral. This percentage will be calculated for caregiver-reported adherence as well as service administrator-reported adherence and concordance among caregiver- and - service administrator reported adherence will be calculated using McNemar's test. Number of barriers to supportive care use will be summarized using descriptive statistics (mean and standard deviation) and compared between intervention and control caregivers using an independent samples t-test.
- 9.2.2 For Objective 2.2.2, we will calculate descriptive statistics by arm and the difference between arms for the variables of interest at T0, T1 and T2, and change in variables from T0-T2 to provide estimates of variance for a larger study. We will examine differences by arm but are not powered for hypothesis testing at a 0.05 alpha-level between the two arms.
- 9.2.3 For Objective 2.2.3, we will examine change in supportive care resource use with change in the caregiver outcome variables (perceived care quality, burden, and distress, quality of life, caregiving self-efficacy, and self-care) using a regression approach to examine whether changes in supportive care resource use are associated with change in the outcomes.

CONNECTing Caregivers to Supportive Services (CONNECT):
A Technology-Based Intervention to Connect Cancer Caregivers with Supportive Care
Resources

Wake Forest Baptist Comprehensive Cancer Center
WFBCCC # 99519

- 9.2.4 For Objective 2.2.4, we will model changes in patient physical well-being and the patient healthcare utilization score at T1 and T2 as a function of change in caregiver psychosocial functioning from baseline using mixed effects models for the outcomes of interest with the baseline value of the outcome, change in caregiver burden and distress, arm, and time as the predictors.
- 9.2.5 A mixed model with a random family effect will also be used to characterize dyadic relationships between patients and caregivers for distress and perceived care quality for Objective 2.2.5.

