9.3 Power and Sample Size

The sample size is based on feasibility, and we draw on our current patient-caregiver head and neck cancer protocol (PI: [name]; IRB00038084) at the WFBCCC, prior recruitment with HNC caregivers,^{13,51,52} and clinic estimates. Our primary feasibility measures are participation, accrual, and retention rates. Assuming a negative binomial distribution and true rate of 50%, the probability that we would approach ≥ 96 dyads to recruit 40 is <0.05 . If we approach ≥ 96 dyads to enroll 40, it is unlikely the true probability is 50% or greater, and we will conclude the study may not be feasible. We anticipate accruing 40 dyads within 9 months (4-5/month). A sample size of 40 achieves 92% power to detect a difference between a mean accrual rate of 4 participants/month and an alternative mean of 3 or fewer participants/month with a significance level of 0.025 using a two-sided one-sample Poisson test. Out of the 40 participants, if the true rate of retention is 70%, we expect 23 or more will be retained (i.e., probability of $n \leq 22$ successes is <0.05); we have 85% power to test that the hypothesis that the rate is 70% compared to 50%.

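### The family-effect model in section 9.2.5 does not reliably deliver the caregiver-patient correlation that objective 3.2.5 asks for

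*Combined protocol and SAP*

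**What the plan says.** Section 3.2.5 sets the target: "To characterize the correlation between caregivers and patients with regard to distress and perceived care quality". The analysis in section 9.2.5, which labels it Objective 2.2.5, is: "A mixed model with a random family effect will also be used to characterize dyadic relationships between patients and caregivers". The sentence then names the same two outcomes as the objective. Nothing further is given.

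The data are longitudinal on both sides. Under Data Collection Procedures in section 7.3, "Caregivers and patients will complete self-report quantitative assessments at T0-T2 through REDCap". The schedule in section 7.2 and Table 2 show both PROMIS distress forms and FAMCARE at all three times for caregivers and for patients.

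The neighbouring section 9.2.4 is more explicit. It names T1 and T2, the baseline value of the outcome, and "change in caregiver burden and distress, arm, and time as the predictors". Section 9.2.5 has no counterpart to any of these.

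**The concern.** The target is one number per outcome: how closely the two members of a dyad resemble each other. A random family intercept measures resemblance among all values that share a family. With three visits per person, those values include repeats from the same person as well as values from partners. Unless a further term separates the two, the model credits a person's own stability to the dyad.

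Two other features remain even at a single visit. A random-intercept variance cannot fall below zero, and with one residual variance the model treats caregivers and patients as equally variable.

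At stake is the only analysis that addresses objective 3.2.5. An unrelated pair of outcomes could be reported as moderately correlated, or an inverse relation as none.

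**Working it through.** The documents give no figure for this analysis, so there is none to reproduce.

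**Inputs from the documents.** Two people per family and three visits (section 7.2), so up to six values per family and outcome; 40 dyads (section 9.3). Section 9.3 also considers the case "if the true rate of retention is 70" per cent; 0.70 x 40 = 28 dyads.

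**Assumptions.** The documents give no correlations or SDs. The within-person correlation across visits, w, is taken as 0.5 to 0.8, with 0.7 as the central case. The true partner correlation, p, runs from -0.3 to 0.5. SD ratios between roles are 1, 1.5 and 2.

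**Reading A: all visits pooled, family intercept, independent residuals.** Six values form 6 x 5 / 2 = 15 pairs. Within-person pairs number 2 x 3 = 6; cross-partner pairs number 3 x 3 = 9. The model fits one common covariance to all 15, so

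ICC = (6w + 9p) / 15 = 0.4w + 0.6p.

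At p = 0 this is 0.4 x 0.5 = 0.20 up to 0.4 x 0.8 = 0.32. At w = 0.7, with simulated REML estimates for 40 dyads alongside:

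| True p | 0.4 x 0.7 + 0.6p | Simulated mean |
|---|---|---|
| -0.30 | 0.10 | 0.10 |
| -0.20 | 0.16 | 0.16 |
| 0 | 0.28 | 0.28 |
| 0.20 | 0.40 | 0.39 |
| 0.30 | 0.46 | 0.45 |
| 0.50 | 0.58 | 0.57 |

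The simulations used 4,000 trials per setting, except the rows at -0.20 and 0.20, which come from a separate run. Results at 28 dyads were nearly the same. This is bias, which more dyads would not remove.

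A person-within-family effect largely removes the mixing: a true 0.30 gave about 0.32 (against 0.48 with the family effect alone in the same runs), and a true 0 gave 0.04 (against 0.27). These rest on 40 runs each with several convergence warnings, so they are approximate. The family variance is still bounded at zero.

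**Reading B: one visit, family intercept, equal SDs, 40 dyads.**

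| True p | Mean ICC | Share of estimates at 0 |
|---|---|---|
| -0.30 | 0.002 | about 97% |
| -0.20 | 0.01 | 89% |
| 0 | 0.065 | about 49% |
| 0.30 | 0.29 | not reported |
| 0.50 | 0.49 | not reported |

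Nothing is mixed here, and non-negative correlations are recovered well. The Pearson correlation at one visit averaged -0.30 for a true -0.30.

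**Reading B with unequal SDs.** For SD ratio k, ICC = 2kp / (1 + k^2). At k = 2 the factor is 4/5 = 0.80, so 0.30 becomes 0.24 and 0.50 becomes 0.40. At k = 1.5 it is 3/3.25 = 0.92, so 0.50 becomes 0.46.

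**Precision for scale.** For r = 0.30 in 40 dyads, the Fisher interval is tanh(0.3095 +/- 1.96/sqrt(37)), about -0.01 to 0.56.

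**The case against.** The sentence names a family effect; it does not say that this is the only covariance term. It follows a mixed model that includes time, and a person effect or correlated residuals would remove most of the blending. A reader might infer that the planned model cannot estimate the partner correlation at all. The documents do not support that: they do not say the visits are pooled, and at one visit with similar variances the model returns 0.29 for 0.30.

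The bound at zero belongs to the usual random-intercept parameterization; an equivalent compound-symmetry covariance allows negative values. The background in section 2.0 describes caregiver and patient well-being as moving together, so a negative correlation is hypothetical. A twofold SD ratio has no support in the documents, and the resulting shift of 0.06 is under half the standard error of about 0.15.

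Nor do the documents show that the next trial would be misdesigned, another inference a reader might draw. Section 9.0 says "For the secondary objectives, quantitative analyses will provide estimates of the mean and variance of CONNECT for acceptability and outcome variables", and no section uses the partner correlation as a design input.

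All of this limits the size of the point. It does not remove it. The literal longitudinal reading is open and strongly biased. The standard form of the model is bounded at zero on either reading. Equal role variances are imposed unless the plan says otherwise.

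**Conclusion.** The point holds in a limited form. Section 9.2.5 does not reliably yield the quantity in objective 3.2.5, and how far off it would be depends on choices the plan leaves open.

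- **Pooled visits with no further covariance term:** a true partner correlation of 0 is reported as about 0.20 to 0.32, given an assumed within-person correlation of 0.5 to 0.8.
- **One visit:** sound for non-negative correlations with similar variances. It cannot show a negative correlation under the standard parameterization, and it is attenuated if the roles' variances differ.

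The large bias therefore rests on a reading of the text and an assumed correlation, neither of which the documents settle. The objective is exploratory, with no test, power statement or decision attached. The change is worth making because it is cheap and this is the objective's only analysis; the trial's primary aims are untouched.

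**What to change.** In section 9.2.5, make the main estimate the caregiver-patient correlation at T0 in all dyads, with its 95% CI, separately for PROMIS anxiety, PROMIS depression and FAMCARE. Section 7.3.2 requires both members to return T0 before randomization, so this estimate is free of arm effects and later dropout. Add the same correlations at T1 and T2.

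If a longitudinal model is also used, specify role-specific means and variances, separate caregiver and patient random intercepts with an unrestricted correlation (or an unrestricted cross-partner covariance), and time and arm as fixed effects. State which parameter is reported as the partner correlation. Fall back to the per-visit correlations if the model does not converge.

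The cost is a few lines of text and no new data. The downside is a few more parameters and possible non-convergence with 28 to 40 dyads, which is why the simple T0 correlation should lead.

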9.3 Power and Sample Size

The sample size is based on feasibility, and we draw on our current patient-caregiver head and neck cancer protocol (PI: [name]; IRB00038084) at the WFBCCC, prior recruitment with HNC caregivers,^{13,51,52} and clinic estimates. Our primary feasibility measures are participation, accrual, and retention rates. Assuming a negative binomial distribution and true rate of 50%, the probability that we would approach ≥ 96 dyads to recruit 40 is <0.05 . If we approach ≥ 96 dyads to enroll 40, it is unlikely the true probability is 50% or greater, and we will conclude the study may not be feasible. We anticipate accruing 40 dyads within 9 months (4-5/month). A sample size of 40 achieves 92% power to detect a difference between a mean accrual rate of 4 participants/month and an alternative mean of 3 or fewer participants/month with a significance level of 0.025 using a two-sided one-sample Poisson test. Out of the 40 participants, if the true rate of retention is 70%, we expect 23 or more will be retained (i.e., probability of $n \leq 22$ successes is <0.05); we have 85% power to test that the hypothesis that the rate is 70% compared to 50%.

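### The 96-dyad feasibility cut-off misses its stated bound of 0.05 by a hair: the exact probability is 0.0501, and 97 is the first cut-off that meets it

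*Combined protocol and SAP*

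**What the plan says.** Section 9.3 (Power and Sample Size) names participation, accrual and retention as the primary feasibility measures. For participation it models the number of dyads approached until 40 are recruited as negative binomial with a true rate of 50%. It then makes two linked statements:

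- The justification: "the probability that we would approach ≥ 96 dyads to recruit 40 is <0.05".
- The rule: "If we approach ≥ 96 dyads to enroll 40, it is unlikely the true probability is 50% or greater". In that case the plan will conclude that the study may not be feasible.

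Both sentences use the inclusive cut-off of 96, and the first attaches a strict bound of 0.05 to it. No computed probability is given.

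**The concern.** The negative binomial is discrete, so moving a cut-off by one dyad changes the tail probability by about 0.01 in this region. It therefore matters whether the cut-off itself is included. The value 96 is the 95th percentile of the number of approaches. A probability below 0.05 is guaranteed for counts above that percentile, not for counts at or above it. The text uses the second form.

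This is the only place in the plan where a numerical result is tied to a conclusion that the study may not be feasible, and it concerns a primary feasibility measure. The cut-off should have the property that is given as its justification.

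**Working it through.** **Inputs, all from section 9.3**

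- Distribution: negative binomial, with T = number of dyads approached until the 40th is recruited.
- Assumed true participation rate: p = 0.50.
- Dyads to recruit: 40.
- Cut-off: T ≥ 96, inclusive.
- Claimed probability: below 0.05.

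**Formula**

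The 40th dyad is reached on approach N or later exactly when the first N − 1 approaches give at most 39 agreements:

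P(T ≥ N) = P(Binomial(N − 1, 0.5) ≤ 39)

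**The plan's own figure (N = 96)**

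P(T ≥ 96) = P(Binomial(95, 0.5) ≤ 39) = 0.050087

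The negative binomial survival function gives the same value. Exact integer arithmetic (the sum of the binomial coefficients C(95, x) for x = 0 to 39, divided by 2^95) confirms that it lies strictly above 1/20, so this is not a rounding effect in the software. The claimed bound is not reproduced.

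**Neighbouring cut-offs**

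| Rule | Equivalent binomial tail | Probability | Below 0.05? |
|---|---|---|---|
| T ≥ 95 | P(Binomial(94, 0.5) ≤ 39) | 0.0607 | No |
| T ≥ 96 | P(Binomial(95, 0.5) ≤ 39) | 0.0501 | No |
| T ≥ 97 (same as T > 96) | P(Binomial(96, 0.5) ≤ 39) | 0.0411 | Yes |

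**Where 96 may have come from**

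P(T ≤ 95) = 1 − 0.050087 = 0.9499 and P(T ≤ 96) = 1 − 0.041097 = 0.9589, so 96 is the 95th percentile of T. Writing ≥ in place of > after looking up that percentile would produce the text as it stands. This is an inference; the plan does not show its calculation.

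A normal approximation (mean 80, variance 80) also falls below 0.05 at 96: 0.0368, or 0.0416 with continuity correction. The plan names the negative binomial, however, and its exact value is easily obtained.

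**Comparison within the same section**

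The retention threshold uses the same strict convention and is correct. With 40 participants and a true rate of 70%, P(X ≤ 22) = 0.032 and P(X ≤ 23) = 0.063, so 22 is the right boundary.

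**How often it would matter**

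The two cut-offs lead to different conclusions only when T = 96. At p = 0.50 this has probability 0.050087 − 0.041097 = 0.00899, or 0.9%. At p = 0.40 it is 3.2%.

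**The case against.** The case for leaving the text alone rests on materiality, and much of it is fair.

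- **Precision.** The excess is 0.000087, and the probability is 0.050 to three decimals. The 50% rate is a round planning value; at 50.1% the same tail is 0.0481. The plan's qualitative inference, that a rate of 50% or more would be unlikely, is as reasonable at 0.0501 as just below 0.05. All of this stands, but the sentence states a strict inequality at exactly 50%, and that inequality is false.
- **Soft consequence.** The rule says only that the study may not be feasible. There is no interim analysis (section 9.6), and the primary analysis is estimation with 95% confidence intervals (section 9.1.1). With 40 recruited, the observed rate is 41.7% (Clopper-Pearson interval 31.7% to 52.2%) at 96 approaches and 41.2% (31.3% to 51.7%) at 97. A reader would take the same view of either. This also stands. At exactly 96 the operational rule is met as written; what fails is the probability that justifies it.
- **Looser counts elsewhere.** Section 9.3 speaks of recruiting 40 in one sentence and enrolling 40 in the next. Section 7.3.2 treats dyads as enrolled only after both members return T0, and allows up to 50 to be recruited so that 40 complete it. Participation is defined on eligible participants (sections 6.1.1.2 and 9.1.1), whereas the rule counts dyads approached. These ambiguities could move the count by more than one dyad, so correcting the cut-off does not by itself make the rule exact. They do not make the probability statement true.

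**Conclusion.** The statement is wrong as written. Under the plan's own distribution, rate, target and inclusive cut-off, the probability is 0.0501, and the first cut-off that satisfies the stated bound is 97, with probability 0.0411. The result needs no assumption beyond those in section 9.3.

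The point is minor: a one-unit error in a decision threshold that alters the conclusion for a single value of the count. The target of 40 dyads, the 9-month accrual estimate, the Poisson accrual calculation and the retention threshold do not depend on it.

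**What to change.** In both sentences of section 9.3, replace ≥ 96 with ≥ 97 or, equivalently, > 96. Stating the probability as 0.041 is optional but would let a reader check the rule directly. If the sponsor prefers to keep 96, describing the probability as approximately 0.05 in place of the strict inequality is enough.

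The cost is a small wording edit to two sentences, with no effect on recruitment, data collection or the analysis programs. While making it, the sponsor could use one term, recruited or enrolled, in both sentences so that the count is unambiguous.

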6.1.1.2 Participation: Proportion of eligible participants who agreed to participate

6.1.1.3 Retention: Number of participants who completed the T2 assessment divided by the number who agreed to participate

CONNECTing Caregivers to Supportive Services (CONNECT):
A Technology-Based Intervention to Connect Cancer Caregivers with Supportive Care
Resources

Wake Forest Baptist Comprehensive Cancer Center
WFBCCC # 99519

6.1.1.3.1 Acceptability: Survey developed for study to assess how much caregivers liked different aspects of CONNECT; and a ~30min (approximately) qualitative interview to further explore acceptability. (Appendices H, I, and J)

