7.3 Intervention Administration

7.3.1 Recruitment

In collaboration with the treating oncologist, patients will be identified through clinic schedules. Screened patients will be recorded in the Subject Screening Form, an excel document (Appendix M) that will be kept on a protected share drive through the Wake Forest Baptist network and is only accessible to key staff members. Patients will be recruited for the study via a mailed recruitment package (Appendix X) or message sent via myWakeHealth that notifies patients that they may be eligible to participate in the study and provides them with an option to opt out of additional contact regarding the study. Patients will then be contacted either by phone or in person (as institutional and government policies allow). At this time additional information will be provided to the patient regarding the study and their eligibility will be confirmed (see section 3.1.2.6).

For patients that are not able to communicate verbally, there is an option in the letter for them to reply to the message with the name and phone number of a caregiver with whom we can discuss the study if they are interested in learning more.

If patient is interested and has an eligible caregiver who is also interested in participating, study coordinator will proceed with consenting them (see section 6.5). If the caregiver is not present, we will seek permission from the patient to contact the caregiver by phone to discuss study participation.

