7.3.2 Randomization Plan

Caregiver participants will be randomized to the CONNECT web-based tool (n=20) or to the generic resource list (n=20) after both the patient and caregiver in a dyad return T0 and will be considered enrolled in the study. We anticipate that some participants may drop out prior to T0, and therefore may recruit up to 50 caregiver-patient dyads to ensure 40 complete T0; this is based on a potential drop out rate of up to 20%, although it is expected be lower. Because this protocol tests a caregiver-delivered intervention, patients will not be directly randomized, though the randomization of a caregiver implies a randomization of a patient. During the enrollment process participants will be informed that they could be randomly assigned to 1 of 2 different supportive treatments (Group A or Group B) with a general description of what these groups will involve, but participants will not be blind to their treatment assignment once they begin the study. Patients will also not be blinded regarding their caregiver's assignment. Allocation to treatment arm will be computer-generated and concealed by [name] (Biostatistician). Study team members will not know group assignment when consenting participants. The Project Manager and PI who assign participants to interventions will be made aware of group assignment after both the patient and caregiver have provided informed consent and returned their baseline questionnaires.

7.3.3 Description and Procedures.

**CONNECTing Caregivers to Supportive Services (CONNECT):
A Technology-Based Intervention to Connect Cancer Caregivers with Supportive Care
Resources**

Wake Forest Baptist Comprehensive Cancer Center
WFBCCC # 99519

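### Section 9.3 sets its 96-dyad feasibility rule on dyads recruited but applies it to dyads enrolled; if the 50% is the agreement rate and the count runs to T0-complete dyads, the stated error rate below 0.05 is not held

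*Combined protocol and SAP*

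**What the plan says.** Section 9.3 introduces participation, accrual and retention as the primary feasibility measures. It then assumes a negative binomial distribution with a true rate of 50% and states that "the probability that we would approach ≥ 96 dyads to recruit 40" is below 0.05. The next sentence turns this into a rule: "If we approach ≥ 96 dyads to enroll 40, it is unlikely the true probability is 50% or greater". In that case the study is judged possibly not feasible. Section 9.3 does not say which rate the 50% is.

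Section 7.3.2 separates the two events. Caregivers are randomized "after both the patient and caregiver in a dyad return T0 and will be considered enrolled in the study". Because some dyads may be lost first, the team "may recruit up to 50 caregiver-patient dyads to ensure 40 complete T0". The section then gives the size of the loss allowed for: "this is based on a potential drop out rate of up to 20%, although it is expected be lower". The same section also uses the word for an earlier stage: "During the enrollment process participants will be informed that they could be randomly assigned".

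Section 6.1.1.2 defines participation as "Proportion of eligible participants who agreed to participate", and 9.1.1 repeats that definition. Participation is therefore about agreement, not T0 return. Its denominator is eligible participants, whereas the 9.3 rule counts dyads approached. Under 7.3.1 patients are first identified from clinic schedules, and at the later contact "their eligibility will be confirmed".

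**The concern.** A cut-off calculated for one event need not keep its error rate when applied to a later and rarer one. If half of approached dyads agree and some of those do not return T0, fewer than half reach enrollment as 7.3.2 uses the word. Reaching 40 enrolled then takes more approaches, and the rule can be triggered although agreement really is 50%.

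This is the only rule in the plan that ends in a feasibility conclusion, and feasibility is a primary objective. On the reading just described, its error rate depends on a pre-T0 loss for which the plan gives only a ceiling. The 50-dyad limit also creates an outcome for which the rule has no answer: 50 dyads agree, but fewer than 40 return T0.

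**Working it through.** **Inputs.** From 9.3: target 40, cut-off 96, true rate 50%, stated probability below 0.05. From 7.3.2: at most 50 dyads recruited, pre-T0 loss L of up to 20%. The values L = 5%, 10% and 15% are assumptions. The calculation also assumes that dyads are independent, that loss is unrelated to how readily a dyad agreed, and that every approached dyad is eligible.

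**1. The plan's own figure.** Let N be the number approached to reach the 40th success, with success probability p. Then P(N ≥ t) = P(Bin(t − 1, p) ≤ 39).

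- t = 96, p = 0.50: P(Bin(95, 0.50) ≤ 39) = 0.0501.
- t = 97, p = 0.50: P(Bin(96, 0.50) ≤ 39) = 0.0411.

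The stated figure is reproduced to rounding. Strictly, it first falls below 0.05 at 97.

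**2. Agreement 50%, count to 40 T0-complete dyads, at most 50 recruited.** Reaching 96 approaches means that after 95 fewer than 50 dyads have agreed and fewer than 40 of those have returned T0:

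P(N ≥ 96) = Σ (a = 0 to 49) P(Bin(95, 0.50) = a) × P(Bin(a, 1 − L) ≤ 39).

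A narrower count keeps only the runs that go on to reach 40 enrolled by the 50th agreement. The chance that 40 are never reached is P(Bin(50, 1 − L) ≤ 39).

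| Pre-T0 loss L | ≥96 approached, all runs | ≥96 approached and 40 enrolled | 50 agree, 40 never enrolled |
|---|---|---|---|
| 0% | 0.050 | 0.050 | 0 |
| 5% (assumed) | 0.124 | 0.124 | <0.001 |
| 10% (assumed) | 0.251 | 0.245 | 0.009 |
| 15% (assumed) | 0.413 | 0.334 | 0.120 |
| 20% (ceiling) | 0.550 | 0.276 | 0.416 |

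Without the 50-dyad limit, p = 0.50 × (1 − L), and the figures at 15% and 20% are 0.430 and 0.626. The limit belongs in the calculation because 7.3.2 sets it. At 20%, the gap between the two counts, 0.550 − 0.276 = 0.274, consists of runs that pass 96 approaches but end without 40 enrolled.

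**3. The other two readings.**

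- *Enroll* in 9.3 means the same as *recruit* (40 agreements): p = 0.50, so 0.0501 as in step 1.
- The 50% is the joint rate of agreement and T0 return: p = 0.50 again, so 0.0501 before the 50-dyad limit is considered. The rule then does not test participation as 6.1.1.2 defines it.

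**4. An example on the step 2 reading.** Suppose 96 eligible dyads are approached, 48 agree, and the 40th T0-complete dyad is the 96th approached. Pre-T0 loss is 8/48 = 17%, within the protocol's allowance. Section 9.1.1 would report participation of 48/96 = 50% (exact 95% CI 39.6% to 60.4%). Section 9.3 would call a rate of 50% or more unlikely.

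**5. Retention, a side issue.** The retention figures in 9.3 are based on 40 participants, while 6.1.1.3 and 9.1.1 divide by all who agreed or consented, up to 50. So 28 completers are 28/40 = 70% or, at the full 20% loss, 28/50 = 56%.

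**The case against.** The strongest reply is that *enroll* simply repeats *recruit*. The two words stand in consecutive sentences with the same 96, 40 and 50%, participation has just been named, and 7.3.2 itself uses enrollment loosely for the consent stage. Read that way, the rule tests agreement, holds about 0.05, and never meets the 50-dyad limit. This stands as a fair reading. The documents do not settle it, because 7.3.2 also ties enrolled status to T0 return.

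A reader might infer that the rule's error rate simply is 0.55. The documents do not support that. The figure needs both conditions (50% as the agreement rate, and a count of T0-complete dyads), the full 20% loss that the protocol expects not to reach, and the inclusion of runs that never enroll 40, which the rule as worded does not cover. Without those runs the figure at the ceiling is 0.28. Up to 10% loss the two counts nearly coincide, so the choice matters little there.

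It is also fair that the consequence is limited. The primary analysis is estimation with 95% confidence intervals, the rule's conclusion is hedged, and no interim analysis is planned. The difference between 96 and 97 is rounding. The 40 in the retention calculation is a planning number, while the analysis denominator is agreement or consent in both places where it is defined.

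**Conclusion.** The wording mismatch is certain: 9.3 calibrates on one event and triggers on another, 7.3.2 distinguishes them, and the 50% is not named. The inflation is conditional. If the 50% is the agreement rate and the count runs to T0-complete dyads, the error rate is about 0.12 at 5% loss and 0.25 at 10% (both assumed), and 0.28 to 0.55 at the 20% ceiling depending on which runs are counted. At the ceiling there is also a 0.42 chance of ending with 50 agreed and fewer than 40 enrolled, which the rule does not address. On either of the other two readings the error is about 0.05.

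It would go too far to conclude that the feasibility results themselves are biased. The estimates and confidence intervals in 9.1.1 do not depend on the rule. Severity lies between minor and should-fix. Confidence is high for the mismatch and moderate for the inflation.

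**What to change.** Use one event and name the rate in 9.3. Suggested text:

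*If 97 or more eligible dyads have been approached by the time the 40th dyad agrees to participate, a true participation rate of at least 50% is improbable (P = 0.041 at 50%), and the study will be judged possibly not feasible.*

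Equivalently, the rule is triggered when fewer than 40 of the first 96 eligible dyads approached agree. This tests participation as defined, aligns the count with the eligible denominator, needs no assumed loss, and is unaffected by the 50-dyad limit. Its chance of flagging is 0.041 at true agreement of 50%, 0.224 at 45%, 0.593 at 40% and 0.896 at 35%.

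If the joint rate was intended, say that the 50% combines agreement and T0 return, use 97, and state what is concluded if 50 dyads agree without 40 returning T0.

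As a minor addition, label the two retention denominators (40 randomized; all who agreed) and report pre-T0 loss as its own proportion with a 95% confidence interval.

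The cost is a few sentences, a cut-off moved by one, and one extra reported proportion. Screened and approached participants are already logged (Appendix M), and agreement and T0 return are already captured, so no new data are needed.
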